#### PFIZER CONFIDENTIAL

[figure not shown]
CT24-WI-GL02-RF023.0 Non-Interventional Study Protocol Template For Secondary Data Collection Study 20-May-2021

Page 20

The study population and characterization of the exposure and comparator groups are illustrated as a flowchart in Figure 2.

Due to the higher estrogen concentration for Premarin VC than non-Premarin LDVEs, higher daily doses of Premarin VC of >0.45 mg/day conjugated estrogen will be analyzed as a separate exposure group (HIRD only, as Premarin VC is not marketed in Sweden). This exposure group is referred to throughout as the HDVC group. Low-dose regimens  $\leq 0.3$  mg/day conjugated estrogen are also indicated for Premarin VC (i.e., 0.5 grams applied daily for 21 days or 0.5 grams applied twice weekly). These low-dose regimens will be evaluated as part of the LDVE exposure group.

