### **Figure 2: Study Population**

Abbreviations: E+P HT, estrogen-progestogen combination hormone therapy; HDVC, high-dose Premarin VC (HIRD only); HIRD, HealthCore Integrated Research Database; LDVE, low-dose vaginal estrogen; MDVE, moderate-dose vaginal estrogen.

Note: Bolded boxes outlined in blue indicate an exposure or comparator group.

The three vaginal estrogen exposure groups and the two comparator groups are described below and summarized in Figure 2 (for definitions of study drugs and gynecological visits, see Section 9.2 Setting and Section 9.3 Variables):

- Exposure 1: New Users of LDVE.
  - o Women who had ≥1 dispensing of an LDVE during the exposure ascertainment period with prescription daily doses ≤10 mcg estradiol or ≤0.3 mg conjugated estrogen at cohort entry and no prior dispensings of vaginal estrogen. Low-dose Premarin VC (HIRD only) is defined as 0.5 g/day dose (equal to daily average strength 0.3 mg or less conjugated estrogens. It should be noted that these women may or may not have used hormone therapy prior to the index date and will be included regardless of such prior use.
- Exposure 2: New Users of MDVE.
  - Women who had ≥1 dispensing of a MDVE during the exposure ascertainment period with prescription daily doses >10 mcg 25 mcg estradiol or >0.3 mg 0.45 mg conjugated estrogen at cohort entry and no prior dispensings of vaginal estrogen. It should be noted that these women may or may not have used hormone therapy prior to the index date and will be included regardless of such prior use. The Swedish cohort will only include subjects with ≥ 1 dispensing of 25mcg estradiol (Vagifem).
- Exposure 3: New Users of HDVC (HIRD Only).
  - Women who had ≥1 dispensing of Premarin VC during the exposure ascertainment period with prescription daily doses >0.45 mg conjugated estrogen at cohort entry and no prior dispensings of vaginal estrogen. It should be noted that these women may or may not have used hormone therapy prior to the index date and will be included regardless of such prior use.
- Primary Comparator: Non-users of vaginal estrogen.
  - Women who had  $\geq 1$  gynecological visit during the exposure ascertainment period, and no dispensings of vaginal estrogen prior to or on the gynecological visit. It should be noted that these women may or may not have used hormone therapy prior to the index date and will be included regardless of such prior use.

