# 9.2.1. Inclusion Criteria

Patients must meet all of the following inclusion criteria to be eligible for inclusion in the study:

1. Women must have  $\geq 1$  study drug dispensing, or  $\geq 1$  gynecological visit, that meets each of the following criteria to be eligible for inclusion in a study cohort (Figure 3; for additional details on study drugs and gynecological visits, see Section 9.3 Variables):

• ≥1 dispensing of vaginal estrogen not indicated for severe vasomotor symptoms or any E+P HT, or a gynecological visit for non-users, from 01 January 2007 through 31 December 2020 (or most recent available date) in the HIRD, and 01 July 2007 – 31 December 2019 (or most recent available date) in Sweden (see Annex 1: Appendix B and Appendix F for vaginal estrogen and E+P HT medications)

Vaginal estrogen: Vaginal estrogen drugs include products which are approved only for one or more symptoms of vulvar and vaginal atrophy due to menopause. Thus, Femring (estradiol acetate vaginal) and Ogen (estropipate vaginal) which are also indicated for moderate to severe vasomotor symptoms, are not included as study drugs. Estrace (estradiol cream) is also excluded due to its indication for vasomotor symptoms and its high concentration of estradiol resulting in greater systemic absorption. Vaginal estrogen study drugs include the following products:

HIRD: Estring, Vagifem, Yuvafem, Imvexxy, generic estradiol (tablet), and Premarin VC;

Sweden: Oestring and Vagifem.

E+P HT: oral, transdermal, or injectable estrogen-progestogen combination hormone therapy products.

Gynecological visit: outpatient office visit with provider specialty of gynecology, or diagnosis/procedural codes for gynecological exam or Pap smear.

2. Female aged  $\geq$ 50 years on the first study drug dispensing date or on the gynecological visit date for non-users (the index date).

3. Minimum required baseline observation period:

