### 9.3.3. Vaginal Estrogen Use

The following drug utilization characteristics will be described during the post-index period for the vaginal estrogen exposure groups:

- Active ingredient at date of first dispensing:
  - o Estradiol vaginal
  - o Conjugated estrogen vaginal
- Formulation at date of first dispensing (vaginal cream, ring, tablet, or insert).
- Duration of use (i.e., duration of all treatment episodes combined).
- Computed for each treatment group as the sum of days in all treatment episodes.

Categorized in the HIRD and Sweden as:

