#### PFIZER CONFIDENTIAL

- 5. HIRD only: To evaluate possible impact of missing information on medical history, we will consider extending the baseline period to 18 months. To assess if there are important differences between the populations with at least 12 months and 18 months of continuous HIRD enrollment, the HR of endometrial cancer will be calculated for LDVE users versus non-users among women who have a baseline period of at least 18 months of continuous HIRD enrollment. Comparing results using different baseline durations will assess the effect of potential misclassification of covariates and the balance with increased random error due to decreased study size (Annex 1: Table 8).
- 6. HIRD and Sweden: To determine if associations between vaginal estrogen, non-users, and E+P HT and endometrial cancer differ according to a patient's history of cancer, a sensitivity analysis will be conducted. to estimate and compare the IRs of endometrial cancer among women by history of cancer other than endometrial cancer and basal cell carcinoma (if case counts are sufficient to support estimation) in the following groups (Annex 1: Tables 9 and 13):
  - a. LDVE new users versus non-users of vaginal estrogen.
  - b. MDVE new users versus non-users of vaginal estrogen.
  - c. HDVC new users versus non-users of vaginal estrogen (HIRD only).
  - d. LDVE new users versus E+P HT new users of hormone therapy.
  - e. MDVE new users versus E+P HT new users of hormone therapy.
  - f. HDVC new users versus E+P HT new users of hormone therapy (HIRD only).
- 7. HIRD only: To identify the rate of endometrial cancer in patients who may have a cumulative exposure that is higher than the intended average daily dose, the rate of endometrial cancer will be estimated among HDVC new users compared to non-users of vaginal estrogen and HDVC new users compared to E+P HT new users stratified by number of dispensings. Number of dispensings will be categorized as ≤ 2 dispensings per year and >2 dispensings per year(Annex 1: Table 10).
- 8. HIRD only: To evaluate possible effects of dose of vaginal estrogen on risk of endometrial cancer among vaginal estrogen new users (the full study population), the HR of endometrial cancer will be calculated for HDVC new users versus LDVE new users (Annex 1: Table 10).

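### Sensitivity analysis 8 is offered as a dose comparison, but HDVC versus LDVE changes active ingredient and formulation along with dose, so its HR cannot be read as a dose effect on its own

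*Protocol*

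**What the plan says.** Section 9.7.4, item 8, for the HIRD only, states its aim as "To evaluate possible effects of dose of vaginal estrogen on risk of endometrial cancer among vaginal estrogen new users (the full study population" and specifies that "the HR of endometrial cancer will be calculated for HDVC new users versus LDVE new users". It states no restriction, stratification or adjustment by product.

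The two groups are made up as follows.

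- **HDVC** (Section 9.1.2, Exposure 3) is a single product: "Women who had ≥1 dispensing of Premarin VC during the exposure ascertainment period with prescription daily doses >0.45 mg conjugated estrogen at cohort entry".
- **LDVE** (Section 9.1.2, Exposure 1) is defined on two ingredients: up to 10 mcg estradiol or up to 0.3 mg conjugated estrogen per day. Section 9.2.1 lists the HIRD study drugs as "HIRD: Estring, Vagifem, Yuvafem, Imvexxy, generic estradiol (tablet), and Premarin VC". Of the low-dose Premarin VC regimens, Section 9.1.2 says "These low-dose regimens will be evaluated as part of the LDVE exposure group".
- **Estradiol cream** is not a study drug. Section 9.2.1 says "Estrace (estradiol cream) is also excluded due to its indication for vasomotor symptoms", and also cites its high estradiol concentration.

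Section 9.7.3.1 plans subgroup analyses by active ingredient and by formulation, each comparing a vaginal estrogen group with non-users.

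**The concern.** A hazard ratio supports a statement about dose only if the groups differ in dose and are otherwise comparable. Here one side is entirely conjugated-estrogen cream. The other is partly estradiol delivered by ring, tablet or insert. Because estradiol cream is excluded, every estradiol user in LDVE differs from every HDVC user in ingredient and formulation as well as in dose tier.

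The protocol itself treats product as a possible source of difference in risk: Primary Objective 3 asks for results by formulation and active ingredient. Item 8 is also the only place where two vaginal estrogen dose groups are compared directly, so its HR is the one most likely to be quoted as the dose answer. A raised HR could come from the cream or the conjugated estrogen rather than the dose. A null HR could conceal a dose effect.

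**Working it through.** **The plan's own figures.** Item 8 has no sizing. The HIRD calculation in Section 9.5.1 concerns LDVE versus non-users: 60 + 239 = 299 events for 80% power at HR 1.5, 1:4 allocation, two-sided alpha 0.05. It reproduces: (1.960 + 0.842)² / [0.2 × 0.8 × (ln 1.5)²] = 7.849 / 0.0263 = 298.4, rounded up to 299. The present point does not depend on it.

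**Composition of the item 8 contrast.**

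| | HDVC | LDVE, Premarin part | LDVE, estradiol part |
|---|---|---|---|
| Ingredient | conjugated estrogen | conjugated estrogen | estradiol |
| Formulation | cream | cream | ring, tablet or insert |
| Daily dose | >0.45 mg | ≤0.3 mg | ≤10 mcg |

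Only the first two columns differ in dose alone. The third differs in all three rows, and its dose is in another unit.

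**Can adjustment separate them?** The baseline covariates in Section 9.3.4 and the propensity score description in Section 9.7.1 do not include index product. Adding it would not help for the full LDVE group. No HDVC woman uses estradiol, so there is no overlap in that stratum, and the only usable information is HDVC against the Premarin part of LDVE.

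**Illustration of size.** Neither input below is in the protocol; both are assumptions.

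- m = share of LDVE person-time on estradiol products, taken as 0.5 to 0.8.
- k = rate ratio of conjugated-estrogen cream to the estradiol products, taken as 1.5 or 0.7.

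Suppose there is no dose effect and the estradiol users have rate λ. The HDVC rate is kλ and the LDVE rate is mλ + (1 − m)kλ. The apparent HR is therefore

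HR = k / [m + (1 − m)k].

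- k = 1.5, m = 0.5: 1.5 / 1.25 = 1.20
- k = 1.5, m = 0.8: 1.5 / 1.10 = 1.36
- k = 0.7, m = 0.5: 0.70 / 0.85 = 0.82
- k = 0.7, m = 0.8: 0.70 / 0.94 = 0.74

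Masking follows in the same way. With a true dose HR of 1.5 and k = 0.7, the apparent HR is 1.5 × 0.70 / 0.85 = 1.24 at m = 0.5, and 1.5 × 0.70 / 0.94 = 1.12 at m = 0.8.

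The distortion vanishes only if k = 1 or m = 0. Restricting LDVE to Premarin VC sets m = 0, so the ratio no longer depends on k.

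**The case against.** The strongest defence is that item 8 works at class level. It says it will evaluate possible effects of dose in the full study population, and it does not promise to isolate dose within a product. The tiers in Section 9.3.1 deliberately span both ingredients and cite dose-conversion references, so HDVC versus LDVE compares the top and bottom of the protocol's own scale. That stands as a reason to keep the contrast. It does not make the HR a dose effect, because the top tier contains only one product.

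Second, much of the within-product information is already planned. Conjugated-estrogen LDVE and MDVE subgroups versus non-users (Section 9.7.3.1), together with primary comparison 1c for HDVC, can be set side by side as a low, moderate and high Premarin gradient. A reader might infer from item 8 that the plan says nothing about dose within Premarin VC; that would be wrong. The gradient is indirect, however. It runs through separately matched sets, and the protocol plans no formal comparison of its steps. It softens the problem without removing it.

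Third, nothing in the protocol shows that k differs from 1, and low-dose Premarin VC sits inside LDVE, so the confounding is only partial. Both are correct.

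Fourth, a Premarin-only comparator is not free of problems. The protocol gives no count for it; the 152,941 in Section 9.5.1 is all LDVE. Tier assignment within one cream also rests on recorded quantity and days' supply. This stands and belongs with the costs of the fix.

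**Conclusion.** The point holds as one of interpretation and specification for a single sensitivity analysis. As written, the item 8 HR combines dose, active ingredient and formulation and cannot be read as a dose effect on its own. That conclusion rests only on the group definitions.

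The size is not known. The figures of 1.20 to 1.36 and 0.82 to 0.74 depend on assumed values of m and k and on there being no other confounding. They show that the distortion could matter in either direction, not that it is present.

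Two stronger readings should be resisted. A reader might infer that the item 8 result is biased in a known direction; the protocol gives nothing from which to derive one. A reader might also infer that the evaluation of Premarin VC required by the regulator is compromised. It is not: high-dose Premarin VC is evaluated as its own group against non-users in primary comparison 1c, and no primary or secondary HR depends on item 8.

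**What to change.** In Section 9.7.4, item 8, and in Annex 1 Table 10, add a comparison of HDVC new users with LDVE new users whose index product is Premarin VC. Re-estimate the propensity score in that subset, and state that this contrast carries the dose interpretation. Moderate-dose Premarin VC users may be added as an intermediate level if counts allow; this is optional. HDVC versus all LDVE can stay, labelled as a product-plus-dose contrast. The listed title of Table 10 mentions only non-user and E+P HT comparators, so it should be extended to cover item 8. The table shell is a separate document and was not available to check.

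No new data are needed. The price is a smaller comparator, whose size the protocol does not give, and hence a wider confidence interval. Dose tiers within Premarin VC would still depend on recorded quantity and days' supply, so some dose misclassification would remain and should be acknowledged in the report.

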#### PFIZER CONFIDENTIAL

estimates of misclassification of covariates to assess potential impact on incidence rate estimates in the PS-matched analysis.

# 9.8. Quality Control

# 9.8.1. HIRD, US

The study will be tracked at various levels to help ensure that all aspects including project delivery, infrastructure, quality processes, resource management, and financial issues are addressed. To help ensure the highest level of quality on every project, HealthCore has established several layers of quality assurance throughout the project lifecycle.

- Role Based Control Checks: Each member of the team is responsible to perform thorough quality control checks on their work; in addition, the Principal Investigator and Research Project Manager are also accountable for the quality of all deliverables.
- Quality Check Points: Regularly scheduled, centralized "checkpoints" have been implemented during the data management cycle to help ensure accurate translation of programming requests.
- Quality Assurance Standards: Standard review procedures have been developed and are applied throughout the project lifecycle.
- Automation: HealthCore has developed standard definitions of many variables and disease states and developed programs to apply these standards as needed on projects. These standards help ensure consistency, repeatability, and accuracy for each project.

HealthCore's research team documents study progress and scientific and quality review of all study activities and deliverables (e.g., protocol, data management, data analysis, reports, manuscripts, etc.) in an Action, Decision, Issue, Notification (ADIN) log and in a Quality Control (QC) log. The ADIN log provides documentation of study progress, action items, issues/issue resolution, and notifications, and is updated weekly during internal project team meetings. The QC log documents the quality control measures performed for each study activity during the conduct of the study.

All programming required for study database extraction and creation of the analytic datasets from the HIRD will be performed in accordance with HealthCore Programming Standards. The HealthCore

#### PFIZER CONFIDENTIAL

Programming Standards are a set of documents describing data extraction methods that are referenced in HealthCore standard operating procedures (SOPs) and provide a guideline for basic, frequently used terms and definitions, and respective coding information to maintain operational consistency. Data validation will occur throughout the data management and analysis process. Data quality checks include, but are not limited to, programming checks by an individual who is not the main programmer for the study, internal dataset consistency, and checks to ensure that Protocol criteria were met. If validation checks are not satisfied, then an examination of the problem will be performed on the dataset or datasets in question and the problem will be resolved.

#### 9.8.2. Swedish Registers, Sweden

For Swedish analyses performed by IQVIA, the study will be conducted according to IQVIA and Pfizer SOPs. Pseudonymized data will be provided to IQVIA investigators in Sweden and a selected subset of designated project members, following signing of a confidentiality agreement, will perform the statistical analysis. Data will be analyzed locally, in accordance with legislation that data cannot be provided outside of Sweden.

At the study level, all aspects of the study from protocol development to the reporting of the results will be conducted within the framework of the IQVIA Quality Management System. A QC plan for the study will be developed and executed, which will include quality control on the study methodology, SAP, programming, data management and analysis, study results, conclusions, and interim and final study reports. Furthermore:

- The study QC plan will establish ownership for the execution of the individual QC steps;
- The Principal in Charge of the study will ensure that individuals responsible for the execution of specific QC steps will have the knowledge, capability, and experience necessary to perform the assigned tasks;
- The result of the execution of the individual steps of the QC plan will be documented and will include the required corrective actions, if any. The execution of any required corrective action will be documented (if necessary);
- The QC plan will be subjected to a final review and approval for sufficiency and completeness from the Principal in Charge of the study;
- Datasets and analytic programs will be stored according to IQVIA procedures with access restricted to study personnel; and
- IQVIA confidentiality agreements are signed by all employees and include data protection and strict prohibitions on re-identification attempts.

#### 9.9. Limitations of the Research Methods

#### 9.9.1. HIRD, US

The HIRD contains a dynamic population in which individuals may enter and exit as their insurance coverage changes over time. Because of this, assessment of vaginal estrogen use is limited to the period during which the individual is enrolled, and it is unknown whether individuals received vaginal estrogen prior to their enrollment. To address this concern, a study design that requires a minimum 12-month observation period prior to the start of follow-up is proposed. Individuals with vaginal estrogen use during this baseline interval will not be admitted to the study. Individuals who had a vaginal estrogen dispensing prior to enrollment may be inadvertently assigned to the non-user group. The effect of this potential exposure misclassification bias will be assessed in a sensitivity analysis restricted to patients with at least an 18-month baseline period.

In this study, diagnosis, procedure, and prescription codes will be used to reconstruct patients' medical histories. Certain risk factors for endometrial cancer such as ethnicity, BMI, pregnancy history, and lifestyle factors are not available in the HIRD or in Swedish registers. The impact of possible residual confounding will be assessed by conducting a quantitative bias analysis.

Possible outcome misclassification due to inaccurate coding of endometrial cancer will be addressed by validation of potential cases using medical records.

Although the HIRD contains a large and geographically diverse population, there are limits to its generalizability. Because the majority of included individuals are commercially insured, most health plan members are currently employed (or are dependents of employed individuals). Findings may not be fully generalizable to individuals receiving Medicaid or Social Security Disability Insurance. Elderly individuals are included in the data environment either due to participation in Medicare Advantage plans, which are administered by Anthem and imply complete data capture in the HIRD, or due to purchase of supplementary insurance. Individuals that purchase supplementary insurance use private programs to help offset the 20% co-pay required for traditional Medicare parts A and B. Because some preventive services are covered in full by Medicare, capture in the HIRD of some diagnoses and procedures may be incomplete and are often excluded from analysis in research studies. Insofar as Medicare Advantage and traditional Medicare individuals may differ from commercially insured patients, our results may have limited generalizability in this age group.

#### 9.9.2. Swedish Registers, Sweden

In the Swedish registers, entry is upon birth or immigration to Sweden and exit from the registers is upon emigration or death.

The Swedish registers used to identify vaginal estrogen use do not have information on daily dose. As a result, when a patient is given a prescription of a known number of vaginal estrogen tablets at a given strength per tablet, it is not clear whether they are to take one or more tablets per day. To determine the length of a treatment episode and the dosage category (LDVE or MDVE), it is assumed that patients are prescribed vaginal estrogen according to the recommended daily dosages. All vaginal estrogens under study available in Sweden are recommended to be used within the low-dose range except for Vagifem, which was available at a MDVE strength per tablet for a limited

